## 4 STUDY POPULATION

### 4.1 INCLUSION CRITERIA

In order to be eligible for participation in this study, the patient must meet all of the following:

#### Age

1. Age  $\geq$ 18 years old.

#### Type of Patient and Disease Characteristics

2. Histologically confirmed ACC with known NOTCH 1/2/3/4 activating mutation that is recurrent or metastatic, not amenable to potentially curative surgery or radiotherapy.
3. Evidence of radiographic or clinical disease progression within 6-months of signing informed consent; newly diagnosed metastatic patients will be allowed.
4. Patients must have FFPE tissue available (please refer to Laboratory Manual for number of slides required). Archived (within 3 years) or fresh core or punch needle biopsied are acceptable.
5. Must have at least 1 target lesion that is measurable per RECIST v1.1 for patients with nodal or visceral metastasis. Patients with bone exclusive disease will also be eligible after consultation and approval with Sponsor's Medical Monitor and only if bone lesions are evaluable and measurable by CT or MRI as per modified MDA Criteria. (see [Table 11](#) in [Appendix C](#)).
6. Resolution of clinically significant toxicities related to prior therapy to National Cancer Institute (NCI) - Common Terminology Criteria for Adverse Events (CTCAE v5.0)  $\leq$  Grade 1, except for sensory neuropathy with resolution to  $\leq$  Grade 2 and alopecia.

#### Sex

7. Male and/or Female.

Contraceptive use by men or women should be consistent with local regulations regarding the methods of contraception for those participating in clinical studies (refer to Section [7.3](#) on contraception). **Refer to Appendix E for country-specific requirements on contraception language.**

8. Women of childbearing potential (WOCBP) must have a negative serum or urine pregnancy test (minimum sensitivity 25 IU/L or equivalent units of HCG) within 24 hours prior to the start of investigational product. An extension up to 72 hours is permissible in situations where results cannot be obtained within the standard 24-hour window.
9. WOCBP must agree to follow method(s) of contraception for the duration of the treatment with AL101 plus post-treatment completion based on country-specific requirements. **Refer to Appendix E for country-specific requirements on contraception language.**

 If an archival tumor block or 25 unstained slides are not available, the patient will be required to have a fresh tumor sample obtained at screening.

10. Men who are sexually active with WOCBP must agree to method(s) of contraception for the duration of treatment with AL101 plus post-treatment completion based on country-specific requirements. **Refer to Appendix E for country-specific requirements on contraception language.**

### **Informed Consent**

11. Capable of giving signed informed consent which includes compliance with the requirements and restrictions listed in the informed consent form (ICF) and in this protocol.

## **4.2 EXCLUSION CRITERIA**

The patient must be excluded from participating in the study if meet any of the following:

### **Medical Conditions**

1. Diagnosed with a malignancy in the past 2 years. However, patients with the following diagnoses may enroll as long as there is no current evidence of disease:
  - a. Non-melanoma skin cancers
  - b. Melanoma in situ,
  - c. Localized cancer of the prostate with current prostate-specific antigen of <0.1 ng/mL,
  - d. Treated thyroid cancer,
  - e. Treated cervical carcinoma in situ
  - f. Treated ductal/lobular carcinoma in situ of the breast.
2. Current or recent (within 2 months of investigational product administration) gastrointestinal disease such as disorders that increase the risk of diarrhea, such as inflammatory bowel disease. Non-chronic conditions (e.g., infectious diarrhea) that are completely resolved for at least 2 weeks prior to starting investigational product are not exclusionary.
3. Evidence of uncontrolled, active infection, requiring systemic anti-bacterial, anti-viral or anti-fungal therapy  $\leq$  7 days prior to administration of investigational product such as known active infection with hepatitis B, hepatitis C (HCV), or human immunodeficiency virus (HIV) at Screening (e.g., positive HIV, HBsAg, HCV RNA at screening).
4. Symptomatic central nervous system (CNS) metastases. Patients with asymptomatic CNS metastases as well as those with previously treated CNS metastases are eligible for enrollment in the study if at least four weeks has elapsed since last whole brain radiation treatment or at least two weeks has elapsed since last focal radiation treatment, steroid therapy is not required, and the patient is deemed clinically stable by the Investigator.
5. Unstable or severe uncontrolled medical condition (e.g., unstable cardiac or pulmonary function or uncontrolled diabetes) or any important medical illness or abnormal laboratory finding that would, in the investigator's judgment, increase the risk to the patient associated with his or her participation in the study.
6. Female patients who are pregnant or breastfeeding.

### **Prior/Concomitant Therapy**

7. Completed palliative radiation therapy  $<$  7 days prior to initiating investigational product.

Confidential

Document State: Effective (Controlled)  
CONFIDENTIAL

Page 37 of 118

8. Prior treatment with gamma secretase inhibitors. Prior treatment with anti-Notch antibodies may be allowed upon discussion with the Sponsor's medical monitor.
9. Last chemotherapy, biologic, or investigational therapy agent <4 weeks or 5 half-lives (whichever is shorter) prior to initiating investigational product; 6 weeks if the last regimen included BCNU or mitomycin C. Prior treatment with investigational monoclonal antibody will be reviewed case-by-case by the Sponsor.

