#### 7.1.4 Prohibited Concomitant Medication

Medications specifically prohibited in the exclusion criteria are not allowed during the ongoing study. If there is a clinical indication for any medication or vaccination specifically prohibited during the study, discontinuation from study therapy or vaccination may be required. The Investigator should discuss any questions regarding this with the Sponsor's Medical Monitor. The final decision on any supportive therapy or vaccination rests with the Investigator and/or the patient's primary care physician. However, the decision to continue the patient on study therapy or vaccination schedule requires the mutual agreement of the Investigator, the Sponsor and the patient.

Patients are prohibited from receiving the following therapies during the Screening and Treatment periods (including retreatment for post-complete response relapse) of this study:

- Prior treatment with gamma secretase inhibitors.
- Note: the following situations are considered 1 line of therapy:
  - *Discontinuation of one drug in a multi-drug regimen and continuation of (an) other drug(s).*
  - *Restarting the same regimen after a drug holiday.*
  - *Switching from IV to oral formulation of the same drug is also considered one regimen.*

Confidential

Document State: Effective (Controlled)  
CONFIDENTIAL

Page 66 of 118

- Exposure to any investigational drug within 4 weeks or 5 half-lives whichever is longer or concurrently with investigational product administration.
- Chronic systemic glucocorticoid use (high dose defined as > 10 mg/day prednisone or equivalent).
- Use of any herbal supplements within 1 week prior to investigational product administration.
- Use of medications causing Torsades de Pointes within 1 week or 5 half-lives (whichever is longer; see [Appendix A](#)).
- Use of strong inhibitors of CYP3A4 within 1 week or 5 half-lives (whichever is longer) or strong inducers of CYP3A4 within 2 weeks or 5 half-lives (whichever is longer; see [Appendix B](#)).
- At least 6 months must have elapsed after prior therapy with any investigational nucleoside analogue.

Patients who, in the assessment by the Investigator, require the use of any of the aforementioned treatments for clinical management should be removed from the study. Patients may receive other medications that the Investigator deems to be medically necessary.

The Exclusion Criteria describes other medications that are prohibited in this study.

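### For prior investigational agents, exclusion criterion 9 and Protocol Section 7.1.4 set different washouts, so a patient eligible under Section 4.2 may breach Section 7.1.4

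*Protocol*

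**What the plan says.** Protocol Section 4.2, exclusion criterion 9, excludes a patient as follows: "Last chemotherapy, biologic, or investigational therapy agent <4 weeks or 5 half-lives (whichever is shorter) prior to initiating investigational product". The same criterion sets 6 weeks where the last regimen included BCNU or mitomycin C. It then adds a separate route for one class: "Prior treatment with investigational monoclonal antibody will be reviewed case-by-case by the Sponsor".

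Protocol Section 7.1.4 opens its list with "Patients are prohibited from receiving the following therapies during the Screening and Treatment periods". One item is "Exposure to any investigational drug within 4 weeks or 5 half-lives whichever is longer or concurrently with investigational product administration". A later item reads "At least 6 months must have elapsed after prior therapy with any investigational nucleoside analogue". After the list, the section says that patients who need "any of the aforementioned treatments for clinical management should be removed from the study". It closes with "The Exclusion Criteria describes other medications that are prohibited in this study".

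These are all current text. Neither the protocol nor the SAP gives one section precedence over the other, and the SAP restates neither washout. The Per-Protocol set is the efficacy evaluable patients without major deviations, as the Sponsor defines them before database lock (Protocol 9.3; SAP 7.2 and 7.3.2).

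**The concern.** The two sections cover the same class, prior investigational agents, and use the same pair of limits, but they choose between the limits in opposite ways. A site that screens against Section 4.2 alone could enrol a patient whom a site applying Section 7.1.4 as well would hold back.

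Two things are at stake. The first is uniform eligibility across roughly 26 planned sites (about 16 in North America and 10 in Europe and Israel). The second is whether such a patient counts as a protocol deviation, since that call can feed into the Per-Protocol set.

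Prior investigational treatment is foreseeable in this population. Pre-screening is allowed while a candidate is on other therapy, and exclusion criterion 14 allows enrolment during the follow-up period of another interventional study.

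**Working it through.** **Inputs.** From criterion 9: 4 weeks (28 days) or 5 half-lives, taking the shorter. From Section 7.1.4: the same two limits, taking the longer. The documents give no half-lives for prior agents, so those below are illustrative assumptions.

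**Formulas**, with h the half-life in days:

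- Criterion 9 window: A = min(28, 5h)
- Section 7.1.4 window: B = max(28, 5h)
- A = B only when 5h = 28, that is h = 28/5 = 5.6 days

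| Assumed h (days) | 5h | A (4.2) | B (7.1.4) | B − A |
|---|---|---|---|---|
| 1 | 5 | 5 | 28 | 23 |
| 2 | 10 | 10 | 28 | 18 |
| 5.6 | 28 | 28 | 28 | 0 |
| 10 | 50 | 28 | 50 | 22 |
| 14 | 70 | 28 | 70 | 42 |
| 21 | 105 | 28 | 105 | 77 |

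**Two worked cases.**

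- h = 2 days, last dose 14 days before Cycle 1 Day 1: 14 ≥ 10, so criterion 9 does not exclude; 14 < 28, so Section 7.1.4 is breached.
- h = 10 days, last dose 35 days before Cycle 1 Day 1: 35 ≥ 28, so criterion 9 does not exclude; 35 < 50, so Section 7.1.4 is breached.

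**Direction.** Because max(28, 5h) is never below min(28, 5h), anyone outside the Section 7.1.4 window is also outside the criterion 9 window. The exception is the BCNU/mitomycin C rule of 6 × 7 = 42 days, which appears only in criterion 9.

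**Antibodies.** Criterion 9 sends prior investigational monoclonal antibodies to case-by-case Sponsor review. Section 7.1.4 covers any investigational drug and has no such route. The long half-life rows should therefore not be read as the way criterion 9 handles an antibody. For that class the mismatch is between discretionary review and a fixed window.

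**Nucleoside analogues.** Section 7.1.4 requires 6 months after an investigational nucleoside analogue. No criterion in Section 4.2 contains that restriction.

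**Scope.** Criterion 9 also covers chemotherapy and biologics. The Section 7.1.4 item names investigational drugs only, so the conflict is confined to investigational agents.

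**The case against.** **Section 7.1.4 is about concomitant medication, not eligibility.** Its title and lead-in point to the Screening and Treatment periods, and eligibility is framed by Sections 4.1 and 4.2. This softens the conflict but does not remove it. The item looks back over a period before AL101 and names concurrent use separately, so it works as a washout.

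**The two rules can both be met.** True: a site applying both would simply use the wider window. The closing sentence of Section 7.1.4 ("The Exclusion Criteria describes other medications that are prohibited in this study") can be read as making the lists cumulative. On that reading, though, criterion 9's choice of the shorter limit would have no effect for investigational agents, and nothing in the documents says that this was intended.

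**The nucleoside-analogue line is not a contradiction.** This stands in part. A restriction in one complementary list and not the other is a mismatch, and a secondary one. As context only, the Amendment 3 summary records that an exclusion criterion was deleted because data did not support excluding nucleoside analogues, so the line in 7.1.4 may be a remnant.

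**Stronger readings that the documents do not support.**

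- A reader might infer that patients inside the longer window must be taken off study. The removal sentence concerns patients who require a listed treatment for clinical management. Someone whose earlier investigational drug has ended does not require it.
- A reader might infer that carry-over from a prior agent inflates ORR, by 1/42 = 2.4 points in Cohort 2 or 1/45 = 2.2 points in Cohort 1 per response. Those figures are only one patient's weight at maximum enrolment. The primary analysis uses the Efficacy Evaluable set, and nothing shows that any patient falls between the windows. Three requirements also limit carry-over without excluding it: progression within 6 months of consent (newly diagnosed metastatic patients excepted), baseline imaging within 28 days before day 1, and confirmation of response at least 4 weeks later.
- A reader might infer that the main result depends on the deviation calls. The Per-Protocol analysis is a sensitivity analysis, and central definition of major deviations before lock limits variation between sites.

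**Conclusion.** The point holds for prior investigational agents. The two sections give different washouts at every half-life except 5.6 days, with no stated precedence, and the conflict runs one way apart from the BCNU/mitomycin C rule. In the table the gap runs from 18 to 77 days away from the point of agreement, but that range reflects the half-lives assumed and is not an estimate for this trial. The antibody and nucleoside-analogue mismatches are secondary.

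The consequences that can be supported are that sites may make different eligibility decisions and that coding for the Per-Protocol sensitivity set is ambiguous. No effect on sample size, power or ORR can be calculated. This is an inconsistency that should be corrected; it does not by itself undermine the primary analysis.

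**What to change.** 1. Reconcile exclusion criterion 9 and Section 7.1.4 to one washout rule for prior investigational agents, and say in that rule whether the case-by-case review of investigational antibodies applies.
2. Make Sections 4.2 and 7.1.4 consistent on investigational nucleoside analogues.
3. State before database lock which rule deviations are coded against, and apply it to every enrolled patient.

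The sponsor must settle the clinical content; no washout length is proposed here. The cost is a protocol clarification and a line in the deviation definitions, with no extra data. The SAP's introduction says it was updated after the dry run and ahead of database lock, so the first two steps probably come too late to change who was enrolled. The third remains useful until lock.

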### Diagnostic Assessments

10. Eastern Cooperative Oncology Group (ECOG) performance status  $\geq 2$ .
11. Abnormal organ and marrow function defined as:
  - a. neutrophils  $<1500/\text{mm}^3$ ,
  - b. platelet count  $<100,000/\text{mm}^3$ ,
  - c. hemoglobin  $<9 \text{ g/dL}$ ,
  - d. total bilirubin  $>1.5 \text{ times upper limit of normal (ULN)}$  (except known Gilbert's syndrome),
  - e. aspartate aminotransferase (AST) and alanine aminotransferase (ALT)  $>2.5 \text{ times ULN}$  OR  $>5 \text{ times ULN}$  for patients with liver metastases,
  - f. serum creatinine  $> \text{ULN}$  and creatinine clearance  $<50 \text{ mL/min}$  (Calculation of CrCl will be based on acceptable institution standard),
  - g. uncontrolled triglyceride  $\geq \text{Grade 2}$  elevations per CTCAE v5.0 ( $>300 \text{ mg/dL}$  or  $>3.42 \text{ mmol/L}$ ).
12. Myocardial infarction within 6 months prior to enrollment or has New York Heart Association (NYHA) Class III or IV heart failure, uncontrolled angina, severe uncontrolled ventricular arrhythmias, or electrocardiographic evidence of acute ischemia or active conduction system abnormalities.
13. Mean QT interval corrected for heart rate using Fridericia's formula (QTcF)  $\geq 480 \text{ msec}$ .

### Other Exclusions

14. Concurrent enrolment in another clinical study, unless it is an observational (non-interventional) clinical study or during the follow-up period of an interventional study.
15. Life expectancy of less than 3 months.
16. Inability to be venipunctured and/or tolerate venous access.
17. Hypersensitivity and/or history of allergy to AL101 and any of its excipients.

### 4.3 PATIENT IDENTIFICATION

Each patient who signed informed consent will be assigned a patient number via the Interactive Web/Voice Response System (IXRS). This number will be used as the primary identification for the complete duration of the study. After the patient has signed the main informed consent form (ICF), the Investigator will enter the patient into the Screening section of the electronic case report form (eCRF).

---

ConfidentialDocument State: Effective (Controlled)  
CONFIDENTIAL

Page 38 of 118

#### 4.4 SCREENING FAILURES

Patients who fail to meet the entrance criteria at any time during the Screening period are defined as screen failures. All screen failures will be recorded on the screening failure log, which documents the site number and screening number and reason(s) for screen failure. The screening failure log will be kept in the Investigator's Site File.

Re-screening/re-assessment outside the Screening period will be possible on a case-by-case basis following Sponsor approval. Patients allowed to be re-screened will be assigned a new screening number (with referral in eCRF to the previous screening number); such patients will be determined a screen failure after the second screening confirmed the patient is ineligible.

#### 4.5 EARLY WITHDRAWAL OF PATIENTS FROM THERAPY OR ASSESSMENT

Patients are free to discontinue their participation in the study at any time and without prejudice to further treatment. The Investigator must withdraw any patient from the study if that patient requests to be withdrawn, or if it is determined that continuing in the study would result in a significant safety risk to the patient.

Discontinuation or interruption of investigational product does not represent withdrawal from the study. Patients may withdraw or be withdrawn from investigational product at any time.

Patients who permanently discontinue investigational product or are withdrawn from the study for non-safety reasons prior to the first efficacy endpoint (i.e., upon 2 cycles of treatment) may be replaced.

Dosing of investigational product must be interrupted for any serious adverse reactions assessed by the investigator as related to investigational product. Restart of dosing may be considered upon approval by the Sponsor's Medical Monitor (or designee) after resolution of IP treatment-related events to baseline.

Please refer to Section [6.6](#) for AL101 dose modifications and toxicity management which may lead to investigational product discontinuation. Pregnancy is a mandatory criterion for permanent discontinuation of investigational product. Any patient being managed with dose interruption for toxicity should have their study assessments followed per SoA.

The patient's participation in the study may be discontinued due to the following reasons:

- Request of Investigator
- Life-threatening event or death
- Patient withdrew consent
- Patient is lost-to-follow-up

The patient may discontinue investigational product due to the following reasons:

- Request of the Investigator
- Adverse event
- Treatment failure
- Patient is non-compliant with study procedures or study protocol

Confidential

Document State: Effective (Controlled)  
CONFIDENTIAL

Page 39 of 118

- Request of Sponsor or regulatory authority
- Pregnancy
- Other (to be specified in the electronic case report form; eCRF)

#### **4.6 HANDLING OF WITHDRAWALS**

If a patient is withdrawn from the study, every effort should be made to determine the reason. This information will be recorded on the patient's eCRF. Patients who withdraw from the study, regardless of cause, should undergo all EOS assessments as specified in Schedule of Activities (SoA; Table 1). Follow-up visits will be scheduled, per protocol.

Patients will be asked to agree to be followed up as stated in the protocol regardless of the reason for discontinuation.

#### **4.7 SPONSOR'S TERMINATION OF STUDY**

The Sponsor reserves the right to discontinue the study at any time for any reason. Such reasons may be any of, but not limited to, the following:

- Lack of efficacy of the investigational product;
- Occurrence of AEs unknown to date in respect of their nature, severity, and duration or the unexpected incidence of known AEs;
- Medical, scientific, ethical, or administrative reasons affecting the continued performance of the study.

Regulatory Authorities also have the right to terminate the study for any reason.

### **5 STUDY PROCEDURES**

- Study procedures and their timing are summarized in SoA in Table 1.
- No protocol-related procedures should be performed before patients provide written informed consent.
- Procedures conducted as part of the patient's routine clinical management and obtained before signing of the ICF may be utilized for screening or baseline purposes provided the procedures met the protocol-specified criteria and were performed within the time frame defined in the SoA.
- Study-related events and activities including specific instructions, procedures, concomitant medications, dispensing of investigational products, and descriptions of AEs should be recorded in the appropriate source documents and eCRF.
- Immediate safety concerns should be discussed with the Sponsor immediately upon occurrence or awareness to determine if the patients should continue or discontinue study intervention.
- Adherence to the study design requirements, including those specified in the SoA, is essential and required for study conduct.

Confidential

Document State: Effective (Controlled)  
CONFIDENTIAL

Page 40 of 118

- All screening evaluations must be completed and reviewed to confirm that potential patients meet all eligibility criteria. The investigator will maintain a screening log to record details of all participants screened and to confirm eligibility or record reasons for screening failure, as applicable.
- For patients who discontinue study therapy early for the reasons specified in Section [4.5](#), an End of Study (EOS) visit will be conducted as specified in SoA (Table 1). Other procedures and evaluations will be completed as deemed necessary by the Investigator.
- For the long-term overall survival status assessment, patients and/or their caregivers will be contacted by phone every 3 months after EOS visit until death, patient withdraws consent or Sponsor terminates the study.
- An unscheduled visit may be performed throughout the study at the patient's request or as deemed necessary by the Investigator. The date and reason for the unscheduled visit will be recorded. The Investigator will monitor AEs and record concomitant medications. Other procedures and evaluations will be completed as the Investigator deems necessary; they may include (but are not limited to) safety laboratory tests, ECG, vital signs and physical examination.

